2.5 Justification of sample size

Sample size is based on the subgroup analysis of patients with primary tumors. The normal approximation to the binomial distribution was used, using continuity corrected Chi square test for proportions, and the following specifications were set:

- a. Randomization rate between the two arms= 1:1

- b. Clinically relevant difference in recurrence detection rates $\geq 10\%$
- c. Significance level (α - two sided) = 5%
- d. Power ($1-\beta$) = 80%
- e. Expected recurrence rate at 1 year in the control arm (Arm B) = 35% (Babjuk et al., 2013).

The required sample size per arm is calculated to be 349 patients, which leads to a total of at least 698 patients needed to detect the difference in proportions stated above for the subgroup analysis of only patients with primary tumors. Since we expect approximately 15% of the patients to be misdiagnosed, and thus not suitable to our research question, the number of patients is inflated with that percentage, leading to 401 patients per arm. Additionally, to allow for a non-compliance rate of 20%, assuming no cross-over and no differential loss to follow up between the arms, the calculated sample size is inflated by 20%, yielding 482 patients per arm. Since approximately $\frac{1}{2}$ of all patients will be patients with primary tumors, this sample size is multiplied by two, leading to a total sample size of 1,928. Sample size calculation was performed using nQuery Advisor 7.0.

TREATMENT OF SUBJECTS

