3.4.9 Study duration (investigator)

The number of centers participating in this study is 15. Each center is expected to recruit 100 patients a year. With the required number of patients being 1928, the estimated recruitment time is approximately one and a half year. Due to the maximum follow up of three years, the total study duration is expected to be four and a half years.

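### Section 2.5 multiplies by 1.15 and 1.20 where it should divide by 0.85 and 0.80, so power for the primary-tumour subgroup is about 77%, not 80%, if the planned losses occur in full

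*Protocol*

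**What the plan says.** Protocol section 2.5 (Justification of sample size) bases the calculation on the subgroup of patients with primary tumours. Its inputs are 1:1 allocation, a 35% one-year recurrence rate in the control arm, a 10-point difference, a two-sided 5% level, 80% power and a continuity-corrected chi-square test. The result is 349 per arm.

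Two allowances follow. About 15% of patients are expected to be misdiagnosed and unsuitable for the research question, so "the number of patients is inflated with that percentage, leading to 401 patients per arm". A non-compliance rate of 20% is then assumed, without cross-over or differential loss to follow-up, and "the calculated sample size is inflated by 20%, yielding 482 patients per arm". Because about half of all patients are expected to have primary tumours, the number is doubled, giving 1,928 over both arms.

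Protocol section 3.4.9 (Study duration, investigator) carries the total forward: "With the required number of patients being 1928".

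Protocol section 2 (Objectives) sets the primary comparison in patients with primary or recurrent disease and describes the primary-tumour analysis as a subgroup analysis. Sections 5.1 and 5.4 specify an intention-to-treat analysis.

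**The concern.** The 15% is a share of the patients who enter, and the 20% is a rate among those enrolled. To keep n patients after losing a fraction d of those enrolled, one enrols n/(1 − d). Enrolling n × (1 + d) always leaves fewer than n, because (1 + d)(1 − d) = 1 − d², which is below 1.

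The first step already shows this. Of 401 patients, 15% lost leaves 401 × 0.85 = 341, which is below 349 before any non-compliance is counted.

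What is at stake is whether the stated 80% power, claimed for the comparison on which the sample size rests, follows from the plan's own assumptions.

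**Working it through.** **Inputs, all from section 2.5:** control rate 0.35; difference 0.10, read as 0.35 versus 0.25 because that direction reproduces the stated figure (0.35 versus 0.45 gives 396); two-sided α = 0.05; power 0.80; continuity correction; losses 15% and 20%; half of patients with primary tumours.

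**Step 1: reproduce 349.** The mean rate is 0.30.
- Uncorrected: n = [1.960 × √(2 × 0.30 × 0.70) + 0.842 × √(0.35 × 0.65 + 0.25 × 0.75)]² / 0.10² = 328.5.
- Continuity-corrected: n′ = (n/4) × [1 + √(1 + 4/(n × 0.10))]² = 348.2, rounded up to **349**.

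The stated figure is right. Power at 349 is 80.1%.

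**Step 2: reproduce 401 and 482.**
- 349 × 1.15 = 401.35, stated as 401.
- 401 × 1.20 = 481.2 (or 349 × 1.15 × 1.20 = 481.6), stated as 482.
- Division gives 349/0.85 = 410.6 and 410.6/0.80 = 513.2. Neither matches, so the plan multiplied.

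**Step 3: apply the plan's losses to its own number.**
- 482 × 0.85 × 0.80 = 327.8, about **328 per arm**.
- Shortfall: 349 − 328 = 21 per arm, or 6%.

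**Step 4: power at that number.** With n = 327.8, SE₀ = √(0.42/n) = 0.0358 and SE₁ = √(0.415/n) = 0.0356.
- Continuity-corrected: Φ[(0.10 − 1/n − 1.960 × SE₀)/SE₁] = **77.4%** (77.5% at n = 328).
- Uncorrected: Φ[(0.10 − 1.960 × SE₀)/SE₁] = **79.9%**.

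**Step 5: full inflation.** 349/(0.85 × 0.80) = 513.2, rounded up to 514 per arm. Then 514 × 2 arms × 2 = **2,056**, which is 128 more than 1,928.

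**Step 6: the all-patient comparison.** 1,928/2 = 964 per arm, and 964 × 0.85 × 0.80 = 655.5. If 35% versus 25% also applies to all patients (an assumption; section 2.5 gives these rates for the subgroup calculation), power is about **97%**, continuity-corrected.

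**The case against.** Several points on the other side carry weight.

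*The primary test is not at risk.* A reader might infer that the trial is underpowered for its primary endpoint. The documents do not support that. The primary comparison in sections 2 and 5.1 covers all patients, and step 6 leaves it well powered under the stated assumption. The shortfall concerns the subgroup.

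*The 77% is one scenario.* A reader might take it as the power of the subgroup comparison without conditions. It assumes that all 15% and all 20% leave the analysis. Sections 5.1 and 5.4 plan an intention-to-treat analysis, so non-compliers may stay in. If only the misdiagnosed patients left, 482 × 0.85 = about 410 per arm would remain, with 86% power at an undiluted effect. Retained non-compliers may, however, dilute the effect. If the difference shrank to 8 points (an assumption, for illustration), power at 410 per arm would be about 67%. The intention-to-treat text therefore makes the power uncertain in both directions. It does not rescue the arithmetic, because section 2.5 itself handles the 20% as a loss of patients.

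*The test matters.* Section 5.1 specifies only a two-sided test. The continuity-corrected test is named for sizing, and without the correction the figure is 79.9%. That limits how serious the point is. It is not a reason to choose the test afterwards so that 80% comes out.

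*The planning inputs are approximate.* The total of 1,928 would still yield 698 evaluable primary-tumour patients if their share were 53.2% (698/(1,928 × 0.68)) instead of one half, and 482 per arm would suffice at losses of 13.0% and 16.7%. This stands as to severity, but the uncertainty runs both ways.

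*Inflating by 20% literally means multiplying by 1.20.* True of the operation, but the stated purpose is to allow for those losses, and the operation does not achieve it.

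**Conclusion.** The inflation in section 2.5 is wrong as written, and the error is minor to moderate. Under the plan's own losses the primary-tumour subgroup keeps about 328 per arm instead of 349. Its power is then about 77% instead of 80%, a shortfall of about 2.6 points.

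This rests on three conditions: complete loss of the 15% and then the 20%; the continuity-corrected test; and 35% versus 25% recurrence in a subgroup that makes up half of those enrolled.

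It would also go too far to conclude that recruitment must rise to 2,056. That is the number the plan's own losses imply for 80% subgroup power. Nothing in the protocol makes 1,928 inadequate for the all-patient comparison.

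**What to change.** Keep the total at 1,928 and amend section 2.5 as follows:

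- Correct the inflation text. State that 482 per arm comes from multiplying 349 by 1.15 and 1.20, and that about 328 per arm remain if 15% and then 20% are lost.
- Restate the subgroup power as about 77% (continuity-corrected) under complete loss, and note that full inflation would give 514 per arm and 2,056 in total.
- Add a sentence that, under the intention-to-treat analysis of sections 5.1 and 5.4, retained non-compliers may dilute the effect rather than reduce the number analysed.

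Do not change the analysis test merely to recover 80%.

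The cost is a few restated figures. No patients are added and section 3.4.9 stays as it is. Should the sponsor prefer to hold 80% power for the subgroup under the stated losses, the price is 128 more patients and an update of section 3.4.9. At that section's planned rate of 15 × 100 = 1,500 patients a year, this adds about one month (128/1,500 = 0.09 year).

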2.6 Investigational treatment

White Light cystoscopy (WL) is currently the gold standard for detecting and treatment of bladder cancer during transurethral resection of the bladder (TURB). Storz Professional Image Enhancement System (SPIES) is a new technique, which visually enhances the contrast between tumor mucosa and healthy tissue, in order to improve the sensitivity of tumor detection.

2.7 Use of co-intervention

Women of childbearing potential are recommended to use the contraceptive pill or intrauterine device during the treatments and for at least one month thereafter. It is a necessity to stop anticoagulation use during the procedure. Anticoagulation can be stopped according to the protocol of the hospital; any deviations from this protocol will be registered.

2.8 Name and description of investigational product

SPIES is a new endoscopic technique which does not require special filters for optimizing visibility of bladder tumors, but instead uses specially designed software to enhance the contrast in the endoscopic image between tumor tissue and healthy tissue. With use of color component processing, the red spectral distribution is suppressed, after which a three-color image is built from the blue and green spectral input. This results in a higher color contrast for differences in the blue and green spectrum, which is related to haemoglobin. Due to its nature and appearance, especially carcinoma in situ (CIS) is expected to be better detectable using SPIES, as compared with WLI. During endoscopy, surgeons can switch between WLI and SPIES and vice versa to study a tumor to their best ability.

2.9 Summary of findings from non-clinical studies

The quality of vision with SPIES has been examined in the iSPIES Study. In this study, urologists were asked to delineate tumors that were shown on images from different modalities of SPIES and WL. Inter and intra-observer variability will be assessed based on an objective measurement. Data from this study is currently being analysed, and will be prepared for publication soon.

2.10 Summary of findings from clinical studies

Diagnostic accuracy is expected to be improved using SPIES compared with WLI, but has not yet been tested clinically.

2.11 Summary of known and potential risks and benefits

The risks patients are subject to in this trial do not differ from risks associated with non-experimental surgery for this condition. Patients will receive the standard treatment in addition to the extra care that is provided to them in the framework of this study. Patients in the experimental arm could have added value from imaging with use of SPIES, since it is expected to improve the sensitivity of the diagnostic tool for assessing bladder cancer.

3. METHODS

3.1 Study parameters/endpoints

3.1.1 Main study parameter/endpoint

- Comparison of the proportions of Arm A and Arm B subjects who undergo TURB for a Ta, T1 or CIS bladder tumor that have a histologically confirmed recurrence found at either three months, one year and three years after TURB.

3.1.2 Secondary study parameters/endpoints

- Peri-operative morbidity (30 days) assessed by the Clavien-Dindo score
- Proportion of re-TUR (defined as within 3 months of initial TURB: this can be a planned TURBT because of resection of high risk tumor, or because of recurrent tumor confirmed at cystoscopy at three months)

3.1.3 Other study parameters

- Baseline characteristics of the patients, such as age or BMI
- Comorbidities, such as Diabetes Mellitus or cardiovascular disease
- Risk factors, such as smoking and use of anticoagulation
- When appropriate: information on previous (adjuvant) treatment, such as type and date of most recent treatment and re-TURs

3.2 Assessment of safety and efficacy

Safety will be determined by assessment of adverse events, vital signs and limited physical examination. In addition, the following will be recorded: complications during surgery, use of bipolar or monopolar TURB, use of platform SPIES (when appropriate), operating time and length of stay.

3.3 Randomisation and treatment allocation

Patients presenting with a bladder cancer and who are scheduled for TURB or patients who are scheduled for random biopsies and/or TURB because of a bladder wash out or voided urine with malignant (G3) cells will be included in the study. Eligible patients who are willing to participate will be randomized in a ratio of 1:1 to either Arm A (SPIES+WLI assisted TURB) or Arm B (WLI assisted TURB). The CROES will utilize the randomization to minimize systematic error and potential selection bias by the investigators. The randomization will be performed by using randomly permuted blocks (computer generated), with block size of 6. To assure balanced characteristics and comparable prognosis between the two arms, the

randomization will be stratified on tumor multiplicity (single or multiple), tumor status (primary or recurrence) and macroscopic findings at time of baseline visit (papillary or solid/flat tumor [including CIS]), leading to 8 stratification groups.

Concealment of treatment allocation is achieved by: 1) reducing the time between randomization and intervention, 2) first deciding whether the patient meets all study entry criteria, and 3) if so, randomize the patient in the DMS. The randomization will take place just before the intervention starts; ideally both occur on the same day. The DMS performs the randomization then reveals treatment allocation. The patients will be blinded to their allocation. Due to the nature of the procedure, the surgeon will not be blinded.

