2.1 Study design

This study is a multicenter randomized controlled trial in which the recurrence rates of cancer between SPIES assisted and WLI assisted TURB are compared. Randomization is stratified by tumor multiplicity (single or multiple), tumor status (primary or recurrent) and macroscopic findings (papillary or flat, where CIS is scored as flat lesion). Patients randomized into the experimental arm (Arm A) will undergo SPIES and WLI assisted TURB, whereas the patients in the control arm (Arm B) will undergo WLI only assisted TURB. WLI is chosen as control, since it is considered the gold standard for detecting bladder tumors. Short and long term follow up will be recorded in order to evaluate the health gains for patients over a longer period. Perioperative (30 days) complications will be compared between the two treatment arms to evaluate the safety of SPIES.

Each participating center must submit this protocol to their local MEC and each participating center is responsible for the insurance of their patients. Data from all participating centers will be collected through electronic Case Report Forms (eCRFs), with use of an online Data Management System (DMS), which is located and maintained at the CROES office.

Members of the CROES office will perform all analyses. Each center willing to participate should have enough experience and be familiar with SPIES. A center is considered to have enough experience when a minimum of 10-20 procedures have already been done with SPIES prior to including patients in this study.

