At three months after surgery, all patients will undergo a routine follow up using WLI cystoscopy. A two-week window will be allowed for the timing of this examination. All visible lesions should be confirmed histologically. Adjuvant treatment will be offered according to the local protocols. When appropriate, information on re-TUR and/or adjuvant treatment will be recorded, as well as adverse events. Information on re-TUR includes reasons for performing this procedure to determine if it was an incomplete resection or a true recurrence found at follow up. Information on adjuvant treatment includes type, timings, time limits and dose.

3.4.4 Intermediate follow up – 6, 9, 12, 18, 24 and 30 months after surgery – Visit 4 to 9

At the time points specified above, all patients will undergo a follow up using WLI cystoscopy. A four-week window will be allowed for the timing of this examination. All visible lesions should be confirmed histologically.

3.4.5 Last study follow up – three years after surgery – Visit 10

At three years after surgery, all patients will undergo a follow up using WLI cystoscopy. A four-week window will be allowed for the timing of this examination. All visible lesions should be confirmed histologically.

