3.4.6 Biopsies and histology

Transurethral resection biopsies will be obtained from all flat lesions and suspicious areas. All papillary lesions must be resected completely. Tissue from the resected lesion(s) will be collected for histological assessment. The findings from both biopsies as well as resected lesions will be registered on a bladder chart and will include presence of lesion, size (defined as the diameter of the largest side of the tumor), type (papillary or flat), number of lesions and location (bladder neck anterior/posterior, trigone, around ureteric orifice right/left, posterior wall, right/left lateral wall, anterior wall, dome). The local pathologist will examine the samples. Staging of the tumors will be done according to the TNM 2009 classification

(Babjuk et al., 2013). Both WHO grading systems will be used for the report (2004 and 1973). For consistency, a standardized pathology procedure will be used to perform the analysis.

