5. STATISTICAL ANALYSIS

5.1 Primary study parameters

The primary end point will be analysed by testing the following hypothesis.

The proportions of patients in either Arm A or Arm B who have recurrence of bladder cancer at one year after TURB will be compared. A two-sided test will be used, with the accompanying null-hypothesis being:

H_0 : The proportions of subjects with recurrence of bladder cancer at one year after TURB are equal for Arm A and Arm B, i.e. $H_0: \pi_A = \pi_B$;
with subsequently, $H_1: \pi_A \neq \pi_B$.

An intention-to-treat analysis will be performed, meaning that all subjects who were randomized will be included in the analyses.

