7.3 Handling and storage of data and documents

The investigator or his/her designee will document all data obtained during the study on the individual eCRFs provided by CROES. Investigators will have access to the DMS, and will receive their own username and password. Only data from their own center is accessible to investigators. Data managers from the CROES will have full access to all data collected during this trial, for purposes of monitoring and analyzing the data. The electronic database will be maintained at the central data collection site selected by the CROES council and shall be updated on a regular basis as determined by the CROES council. A manager, selected by the CROES council, at the central data collection site will maintain and coordinate the data collection. As determined by the CROES council, all PIs will receive feedback on the data collection regularly. This also applies to information on patients who underwent baseline examinations required for inclusion to the trial, but who were not included in the study.

Patient data will be entered anonymous, the key to coded information is held at each study center for its own patients and is the responsibility of the local PI. All requested information

must be entered into the electronic case report form and on datasheets or in the medical records. Data entered into the DMS is fully encrypted and therefore anonymized for all participants. Subjects are to be identified by subject number, birth year and center number. Any correction in datasheets should be made by striking through the incorrect entry with a single line and then entering the correct value adjacent to the incorrect entry. The correction must be initialed and dated by the person making the correction. The completed eCRF must be signed or authorized by the investigator. The investigator will retain source documents for 15 years in a location which is secure and to which access can be gained if required. The following documents will be archived: investigator file, CRFs and medical records. Handling of personal data is in compliance with the Dutch Personal Data Protection Act.

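### Minor, cheap improvement: the primary comparison in 5.1 has no term for the randomisation factors or for centre, which forgoes a little precision but does not threaten the stated power

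*Protocol*

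**What the plan says.** **Randomisation.** Section 2.1: "Randomization is stratified by tumor multiplicity (single or multiple), tumor status (primary or recurrent) and macroscopic findings". Section 3.3 repeats the three factors, "leading to 8 stratification groups", and uses "randomly permuted blocks (computer generated), with block size of 6". Two levels each give 2 × 2 × 2 = 8, so there is no room for centre. The stated aim in 3.3 is arms with balanced characteristics and similar prognosis.

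**Primary comparison.** Section 5.1 says that the proportions of patients "who have recurrence of bladder cancer at one year after TURB will be compared". The test is two-sided, of equal proportions in Arms A and B, on all randomised subjects. No covariate, stratum or centre is mentioned. The only named test is the continuity-corrected chi-square in the sample size section (2.5). Surgeon experience and geography appear only in 5.3, among other study parameters.

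**What is local.**
- Adjuvant treatment (3.4.3): "Adjuvant treatment will be offered according to the local protocols". Section 3.5 leaves it to the local investigator and only recommends standardisation by risk group.
- Histology (3.4.6): "The local pathologist will examine the samples". A standardised procedure is promised, but no central reading.
- Surgery: by each site's own unblinded surgeons. SPIES experience is judged per centre (2.1), and the SPIES platform and resection modality are left to the investigator (3.5).

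**What is recorded.** Section 7.3: "Subjects are to be identified by subject number, birth year and center number".

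**The concern.** The endpoint is histologically confirmed recurrence. How completely the tumour is resected, which adjuvant policy follows and who reads the slides can each move it, and each is set by the centre. If recurrence differs between centres, an analysis without a centre term leaves that variation in its error. The randomisation does not force the arms to be even within a centre, so chance imbalance adds to it.

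The same holds for the three tumour factors. The protocol thinks them prognostic enough to stratify on, and its introduction links recurrence to the number of tumours, but 5.1 does not carry them into the analysis. Leaving stratification factors out of the test tends to make it slightly conservative.

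At stake is precision, chiefly in the primary-tumour subgroup on which the trial was sized.

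**Working it through.** **1. Reproduce the plan's figure (2.5).** Inputs: 35% v 25%, two-sided 5%, 80% power, and "Randomization rate between the two arms= 1:1".
- Without continuity correction: n = [1.960·√(2·0.30·0.70) + 0.842·√(0.35·0.65 + 0.25·0.75)]² / 0.10² = (1.270 + 0.542)² / 0.01 ≈ 328.5, so 329.
- With it: (328.5/4)·[1 + √(1 + 4/(328.5·0.10))]² ≈ 348.2, so **349 per arm**, as stated.
- Then 349 × 1.15 = 401, 401 × 1.20 = 481.2 (482), and 482 × 2 × 2 = **1,928**, as stated.

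At 349 per arm, the uncorrected crude test has 82.3% power.

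**2. Imbalance within centres.** Section 3.4.9 gives 15 centres; equal size is assumed.
- Primary-tumour subgroup: 698/15 ≈ 46.5 per centre. The Arm A share has a 95% range of 0.5 ± 1.96 × 0.5/√46.5, or 36% to 64%. With 46 patients, a 60:40 or worse split (18 or fewer, or 28 or more, in Arm A) has binomial probability 0.18: 15 × 0.18 ≈ 3 centres.
- All patients: 1,928/15 ≈ 129 per centre, range about 42% to 58%.

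**3. Power with and without centre.** The between-centre SD on the logit scale is not in the documents, so a range is assumed. Simulation: 20,000 trials per setting, 349 per arm, marginal rates held at 35% and 25%, allocation not stratified by centre. The SD 0.8 row is from a 4,000-trial run that also used blocks of 6 in eight strata.

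| Assumed SD | 95% of centre control rates | Crude, corrected | Crude, uncorrected | Mantel-Haenszel by centre | Gain over uncorrected |
|---|---|---|---|---|---|
| 0 | 35% | 80.6% | 82.9% | 81.9% | −1.0 |
| 0.3 | 23–49% | 79.5% | 82.0% | 81.6% | −0.4 |
| 0.5 | 16–58% | 80.5% | 82.7% | 83.8% | +1.1 |
| 0.7 | – | 80.0% | 82.2% | 84.9% | +2.7 |
| 0.8 | 9–70% | – | 82.4% | 86.2% | +3.8 |
| 1.0 | 6–77% | 79.9% | 82.1% | 87.2% | +5.1 |

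Other runs of the same design gave gains of −0.6 to −0.7 at SD 0, −0.2 to −0.8 at 0.3, +0.6 to +1.2 at 0.5, +2.3 to +2.7 at 0.7 and +4.4 to +5.3 at 1.0. They agree within simulation error.

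**4. Check by formula.** The binomial variance p(1 − p) is the total variance, so it already contains the between-centre part. Stratifying removes that part, a fraction ICC of the total, and costs about one patient in 46.5 through uneven splits (factor 1 − 1/46.5 = 0.979). The crude standardised effect is 1.960 + 0.928 = 2.888, from 82.3% power. The stratified one is 2.888·√[0.979/(1 − ICC)]. The ICCs for SD 0, 0.3, 0.5 and 0.8 are 0, 0.020, 0.052 and 0.116, giving power of 81.5%, 82.3%, 83.5% and 86.0%, in line with the table.

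**5. Type I error.** With 35% in both arms, the uncorrected crude test rejects in 4.4% to 5.5% of trials across SD 0 to 0.8, and the Mantel-Haenszel test in 4.7% to 5.5%. There is no inflation.

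**6. Full population.** With all 1,928 analysed and the same 35% v 25%, power is at least 99.8% for both tests at every SD from 0 to 0.8.

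**The case against.** **It belongs in the SAP.** Section 7.2 foresees a SAP. Section 5.1 names no test and does not call the comparison unadjusted; a centre-stratified test addresses the same null hypothesis. This largely stands: one can say only that the comparison as written has no such term, not that the final analysis will lack it.

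**The gain is small where it is plausible.** At SD 0.5 the centre rates already span 16% to 58%, close to the 15% to 61% range that the introduction quotes and attributes to tumour characteristics rather than centre. A 5-point gain needs centre rates from about 6% to 77%, which nothing in the protocol supports. This stands.

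**There are mitigations.** The pathology procedure is standardised, adjuvant standardisation is recommended and SPIES experience has a minimum. These should narrow centre differences, but none puts centre into the analysis.

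**Stronger readings that a reader might infer, and why they fail:**
- *The trial is underpowered.* The continuity-corrected test used for sizing stays at about 80% at every assumed spread, because its variance already includes the between-centre part.
- *A positive result could be a centre artefact.* Allocation is random and type I error is nominal, so the test already allows for chance imbalance between centres.
- *Randomisation should have been stratified by centre.* That would give 8 × 15 = 120 cells of about 16 patients each. With a fixed block of 6 and an unblinded surgeon, allocation would become easier to predict. Leaving centre out of the lists is defensible.

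**Conclusion.** The point holds as a minor, inexpensive improvement. As written, 5.1 uses neither the randomisation factors nor centre, although all are recorded and the local conduct of surgery, adjuvant treatment and pathology makes centre differences plausible. In the primary-tumour subgroup, centre adjustment is worth nothing at a logit SD of 0.3, about 1 point of power at 0.5, 2 to 3 at 0.7 and about 5 at 1.0. It costs up to about 1 point if centres are alike. In the full trial it makes no practical difference to power.

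These sizes rest on 15 equal centres, normal centre effects on the logit scale, the same treatment effect on that scale in every centre, and 349 evaluable per arm. The number of centres is itself not settled: 3.4.9 says 15, while 7.2 describes one principal investigator per centre but 11 committee members. The figures cover centre only. Any further gain from the three tumour factors cannot be sized, because the protocol gives no recurrence rates by stratum.

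**What to change.** Add to 5.1 that the primary comparison is adjusted for tumour multiplicity, tumour status, macroscopic findings and centre. One workable form is a logistic model with the three factors as fixed effects and a random centre intercept, reported as a marginal risk difference with its confidence interval. This stays on the scale of the stated hypothesis and avoids 120 sparse strata. In the primary-tumour analysis, tumour status is constant and drops out. Fix any rule for pooling small centres before unblinding. Keep the unadjusted comparison as a sensitivity analysis. Leave the randomisation lists unchanged. If the SAP already specifies such an adjustment, a cross-reference in 5.1 is enough.

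Cost: a sentence or two, modest extra analysis work, and at most about 1 point of subgroup power if centres do not differ. It should be settled before unblinding, since an adjustment chosen later would look data-driven.

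### Only the patient is blinded: nothing requires the follow-up cystoscopist or the local pathologist to be unaware of the arm, which leaves the 12-month recurrence comparison open to detection bias that can be reduced cheaply

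*Protocol*

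**What the plan says.** The protocol's blinding statements are both in section 3.3. On patients: "The patients will be blinded to their allocation". On operators: "Due to the nature of the procedure, the surgeon will not be blinded".

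The main endpoint in section 3.1.1 compares the proportions of patients "that have a histologically confirmed recurrence found at either three months, one year and three years after TURB". Section 5.1 fixes the primary test at one year, with the null hypothesis: "The proportions of subjects with recurrence of bladder cancer at one year after TURB are equal for Arm A and Arm B".

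Recurrence is found as follows:

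- At three months (section 3.4.3), "all patients will undergo a routine follow up using WLI cystoscopy".
- At the later visits (sections 3.4.4 and 3.4.5), "all patients will undergo a follow up using WLI cystoscopy".
- At each of these visits the rule for tissue is: "All visible lesions should be confirmed histologically".
- On reading the tissue (section 3.4.6): "The local pathologist will examine the samples". The same section calls for a standardised pathology procedure, TNM 2009 staging and both WHO gradings.

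The protocol does not say who performs the follow-up cystoscopy, whether that person may be the operating surgeon, or whether the examiner or the pathologist is kept unaware of the arm.

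**The concern.** Recurrence is counted only after two steps: an examiner calls a lesion visible and takes tissue, and a pathologist then calls it tumour. The first step depends on judgement and effort, and the protocol leaves it open to someone who knows the arm. An examiner who shares the protocol's stated expectation that SPIES lowers recurrence (Summary and section 1) could search less closely, or accept a borderline area as normal more readily, in Arm A. Any such difference passes straight into the 12-month comparison.

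Two further judgements are also left to staff who may know the arm: whether a re-TUR reflects incomplete resection or true recurrence (section 3.4.3), and whether visits are scheduled more often than planned (section 3.4.8).

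No analysis can restore masking afterwards. Who examines and what they are shown are conduct rules, so they belong in the protocol rather than in an analysis plan.

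**Working it through.** **1. Does the stated reason for not blinding reach follow-up?**

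| Step | Modality | Is the allocation needed to do it? | Masking stated? |
|---|---|---|---|
| Index TURB (3.5) | SPIES and WLI in A, WLI in B | Yes | Surgeon expressly not blinded |
| Follow-up cystoscopy (3.4.3 to 3.4.5) | WLI in both arms | No | Nothing stated |
| Reading follow-up tissue (3.4.6) | Same in both arms | No | Nothing stated |

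The reason given in section 3.3 applies to the first row only.

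**2. The plan's own sample size (section 2.5)**

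Inputs: 35% against 25%, two-sided alpha 5%, power 80%, 1:1 allocation, continuity correction.

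- Uncorrected: n' = [1.960·√(2·0.30·0.70) + 0.842·√(0.25·0.75 + 0.35·0.65)]² / 0.10² = 328.5.
- Corrected: n = (n'/4)·[1 + √(1 + 4/(n'·0.10))]² = 348.2, so 349 per arm, as stated.
- Inflation: 349 × 1.15 = 401; 401 × 1.20 = 481.2, stated as 482; 482 × 2 arms × 2 = 1,928, as stated.

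Masking enters none of these inputs, so the fix leaves the sample size unchanged.

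**3. Illustration of sensitivity to differential ascertainment**

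Assumptions, none of them supplied by the documents as facts about bias:

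- There is no true effect.
- Observed recurrence is 35% in Arm B. The figure is from section 2.5, where the calculation rests on primary tumours; here it is applied to all patients.
- Ascertainment in Arm A is 1, 2 or 3 percentage points lower.
- Patients per arm: 1,928/2 × 0.85 × 0.80 = 655.5, taken as 656.

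The chance of a significant result favouring SPIES is

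P = Φ[(d − 1.960·SE₀)/SE₁],

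with d = pB − pA, p̄ = (pA + pB)/2, SE₀ = √(2p̄(1−p̄)/n) and SE₁ = √(pA(1−pA)/n + pB(1−pB)/n), without continuity correction.

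For pA = 0.33 and n = 656: SE₀ = 0.02616, SE₁ = 0.02615, and (0.02 − 0.05127)/0.02615 = −1.196, so P = 11.6%.

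Because the number analysed is itself uncertain, the table also uses the primary-tumour target (349), twice that target (698) and all randomised patients (964).

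| Shortfall in Arm A | n = 349 | n = 656 | n = 698 | n = 964 |
|---|---|---|---|---|
| 0 | 2.5% | 2.5% | 2.5% | 2.5% |
| 1 point | 4.6% | 5.7% | 5.9% | 6.7% |
| 2 points | 8.0% | 11.6% | 12.1% | 15.1% |
| 3 points | 13.1% | 20.9% | 22.0% | 28.6% |

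If Arm A were instead over-ascertained by 1, 2 or 3 points, the same formula with the sign of d reversed and n = 656 gives false significance against SPIES of 5.7%, 11.4% and 20.3%.

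**The case against.** The strongest reply is that the protocol already limits this bias. Patients are blinded, the visit schedule and the follow-up modality are the same in both arms, every visible lesion is to be confirmed, recurrence needs histology, and pathology follows a standardised procedure. This stands in part. These rules guard well against false positives and narrow the discretion over what to biopsy. They do not govern how hard the examiner looks, or when an area counts as a visible lesion.

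The pathology half is the weaker one. Follow-up tissue is taken after WLI in both arms, so the follow-up examination itself reveals nothing about the arm. The allocation would have to be carried over from the index record. That lowers the risk without excluding it.

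The direction of bias is not established either. An examiner who knows that extra sites were mapped with SPIES might look harder in Arm A, which would work against SPIES.

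A reader might infer more than the document supports:

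- That the plan assigns follow-up cystoscopy to the operating surgeon. It is silent on who performs it.
- That pathology requests or follow-up data pages show the arm. Neither form is described, and nothing says that a bladder chart goes to the pathologist. Form layout and system display may be settled in operational documents that are not shown.
- That the bias could be removed at no cost. The protocol costs nothing of the kind. Where the operating surgeon is the only examiner available, hiding the allocation on a screen does not undo what that surgeon knows.

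**Conclusion.** The concern holds in limited form. The protocol does not require either person who determines the primary outcome to be unaware of the arm, although neither needs to know it. The 12-month comparison is therefore open to detection bias, chiefly through search effort and the threshold for calling a lesion visible. The bias can be reduced at low cost, but not eliminated.

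The percentages show how sensitive the test is to an assumed bias. They are not evidence that such a bias exists, nor of its size or direction. What they support is that a shift of 1 to 3 points, small beside the 10-point design difference, raises the one-sided false-positive rate noticeably at every plausible number analysed.

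This is a worthwhile, inexpensive improvement to the conduct rules, not a fatal flaw.

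**What to change.** State in sections 3.3 and 3.4.3 to 3.4.6 that:

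- (a) pathology requests for follow-up specimens carry neither the arm nor the imaging modality used at the index TURB;
- (b) the data management system does not display the allocation on follow-up pages;
- (c) where the existing roster allows, follow-up cystoscopy is done by a urologist who did not perform the index TURB and is not told the arm, and the eCRF records at each visit whether the examiner knew the arm, to support a sensitivity analysis.

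The cost is protocol wording, one added eCRF item, and a change to a form and to the display of a system that the coordinating office sets up and maintains itself (section 7.9). No extra staff or procedures are needed and the sample size is unchanged. The limits should be stated openly: (c) will not be possible at every visit, and the arm may still be learned from hospital records.
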